## **OPTIMIZING DISCHARGE AFTER EMERGENCY DEPARTMENT VISITS FOR CHILDREN WITH UNCONTROLLED ASHTMA**

**Version 9-28-18**

**PROJECT SUMMARY:** The objective of this project is to develop a systematized method to prescribe inhaled corticosteroids (ICS) to children with uncontrolled asthma after an emergency department (ED) visit. ICS are indicated for children with uncontrolled asthma according to national guidelines, but it is unclear if prescription of ICS in the emergency department setting results in improved outcomes. Currently, ICS prescriptions are provided infrequently (<5% of visits for children with asthma). We will systematize ICS prescription using the Pediatric Asthma Control and Communication Instrument (PACCI), which we have demonstrated is a useful tool for ED clinicians to rapidly assess asthma control. The PACCI is easy to use, can be completed by families, and contains an algorithm that helps clinicians decide when ICS are indicated. We will use a randomized controlled trial (RCT) to compare asthma morbidity in children receiving ICS prescription to children receiving routine asthma care.

**PROJECT BACKGROUND:** Asthma is a common pediatric illness and results in significant morbidity and health care costs.(1) Use of ICS for children with persistent level asthma has been demonstrated to reduce symptom frequency and improve quality of life.(2, 3) Frequently children that meet criteria for ICS use are not using these medications; this is particularly true of children who visit EDs for acute asthma exacerbations.(4) ED visits are ideal for interventions in children, as during these visits, parents are receptive to interventions because of heightened concern based on the acute, visible manifestations of the child's asthma.

Interventions for families of children with asthma have been attempted in the ED but have not consistently demonstrated improvement in long-term asthma-related outcomes.(5-11) Despite these equivocal results, many experts continue to emphasize the role of ED clinicians in preventative care,(12, 13) with a focus on improving chronic asthma management.(14, 15) Several recent publications have identified ICS prescriptions by ED clinicians for uncontrolled asthma as a feasible intervention that is likely to benefit children.(16-18) This is potentially effective given that ED visits for children with asthma often indicate high-risk asthma.(19, 20) Also, children that visit EDs are less likely to have a regular source of care for asthma,(4, 21) more likely to have poorly controlled asthma,(17, 22) are less likely to be using appropriate controller medications,(4) and often belong to underserved populations that are at risk for asthma-related morbidity.(21, 23-27) ED visits for children with asthma also represent a teachable moment.(13, 28) Manifestations of asthma are most salient at these visits, and parents may be more receptive to interventions to improve disease management. Because parents often view asthma as episodic rather than chronic in nature, they may be less likely to follow through with interventions when disease manifestations are not as readily apparent.(29) All

of these factors contribute to the ED being an important setting for interventions to improve disease management. The goal of this research plan is to optimize the delivery of ICS prescriptions using a standardized tool (PACCI) to identify children with uncontrolled asthma. Our second goal is to develop an educational component to be delivered at the time of ICS prescription to enhance subsequent medication adherence.

In a recent study using the National Hospital Ambulatory Medical Care Survey (NHAMCS), we demonstrated that ICS are prescribed during only 4% of pediatric asthma visits at U.S. EDs, despite approximately 800,000 visits for pediatric asthma annually.(18) We also calculated that ICS prescriptions are indicated in 20%-23% of ED visits for children with asthma exacerbations. These figures indicate that nationally, a systematized approach to prescribing ICS for children with uncontrolled asthma in the ED could result in 150,000 children per year having an appropriate first-line controller medication prescribed after an ED visit.

After identifying prescription of ICS as a potential intervention, we investigated a mechanism to facilitate use of this strategy in the ED setting. We validated use of the PACCI in the ED in collaboration with colleagues at Johns Hopkins. The PACCI allows clinicians to rapidly assess chronic asthma control based on responses to questions about asthma over sub-acute (1-2 weeks) and longer (12 month) time periods.(30) Our preliminary validation of the PACCI in 56 children with asthma in our ED has shown that it is: 1) Effective (accuracy of ED clinicians at identifying poorly controlled asthma was 95% with PACCI versus 56% without,  $P=0.03$ ), and 2) Raises awareness of the need to assess chronic asthma control during ED visits, based on feedback from ED clinicians in the study.

#### **PROTOCOL:**

**Participants:** This study will include a convenience sample of children who present to the ED with an asthma exacerbation when research staff is present. Potential participants will be identified by research nurses who encounter children with complaints of "asthma exacerbation", "wheezing", "cough", "dyspnea" or "shortness of breath". We plan to enroll 143 children 3-12 years old who: 1) have physician-diagnosed asthma based on parental report, and 2) are not already using an ICS. Exclusion criteria will include: 1) Previous participation in the study, 2) Co-morbid

cardiorespiratory disease (e.g.: cystic fibrosis), 3) If the parents do not speak English, or 4) If the children are hospitalized.

If the child is eligible, a member of the research team will approach the family to obtain informed consent for study participation. Informed consent will include permission to review the child's medical records and pharmacy records using the standard release of information forms used in the Hasbro ED. After consent, the participant and their family will complete the PACCI. If the responses indicate that they have "controlled" asthma then they will be excluded from further study procedures, otherwise they will be eligible for the study procedure and will be randomized (see Randomization below). For each participant, the following demographic/clinical data will be collected: date of birth, date of ED visit, gender, race/ethnicity (using NIH reporting guidelines),(31) family socioeconomic status (using the National Opinion Research Council system(32)), income-to-needs ratio,(33) insurance, ETS exposure, name of the child's primary doctor, name/location/phone number of child's primary pharmacy, and family contact information. A baseline quality of life score will also be obtained using the Integrated Therapeutics Group Child Asthma Short Form (ITG-CASF). Treatment by the ED staff during the visit will not be affected by study participation. After data collection, researchers will inform parents of the follow up schedule, and pro-rated compensation (\$10 for the one week doser CT delivery visit, \$10 for the one month Doser CT retrieval visit, and \$20 for completion of the 6 month follow-up phone calls).

**Randomization:** Participants will be randomized to the ICS prescription arm or the routine asthma care arm. We will use block randomization to balance the number of participants in each arm, and varied block sizes (4 – 8) because of incomplete blinding of assignments. The allocation ratio between intervention and control arms will be 1:1. Random treatment assignments in each block will be generated in advance using a computer algorithm. Assignments will be placed in sealed, opaque, consecutively numbered envelopes by a person not involved in the study. When a participant is enrolled, the RA will take the next envelope, record the envelope study ID for that participant, and open the envelope to determine the assignment.

**ICS Prescription Arm Protocol:** Participants in the ICS prescription arm will follow the treatment plan, discharge instructions, and follow up recommendations provided by the treating clinicians while they are in the ED. During discharge, the study nurse will provide the asthma discharge instructions (see attached instructions) to the family and inform them that the child has met criteria for prescription of an ICS to help control the asthma. The families preferred pharmacy will be determined and a prescription for the first-line ICS covered by the participant's insurance will be called in within 24 hours by the study PI or co-Investigator (both licensed clinicians). Dosing will follow the recommendations outlined in the NHLBI asthma guidelines for low dose ICS in this age group for the respective medication.(19) In addition to the standard instructions, the nurse will give specific instructions for ICS use including how to administer medication, use of

spacer devices to be used with the MDI, recommendations for daily use, possible side effects of medication use, and distinction between controller and quick-relief rescue medications. Parents will be informed that they should follow up with their primary care provider to discuss the length of ICS use.

One week after study enrollment, the pharmacy to which the prescription was called will be contacted to determine any prescriptions for asthma medications that were filled. Delivery of a doser CT device, which is used to assess medication adherence, will occur approximately one week after study enrollment. This device will be coupled with the ICS MDI (if one was obtained from the pharmacy) or with an albuterol MDI (if no ICS was filled). Families will be called two weeks after the ED visit to determine if there are any issues with device use. To ensure proper communication, a checking-in mailer will be sent out two weeks post-enrollment. This mailer will serve as a reminder to contact staff if participants encounter any issues with the doser CT device or if their contact information has changed. A home visit will be scheduled at one month to arrange for retrieval of the doser CT device. An "Unable to Contact Mailer" will be sent out to participants if staff are unable to contact them after several attempts.

**Routine Asthma Care Arm Protocol:** Participants in the routine asthma care arm will follow the treatment plan developed by the treating clinicians as part of routine care. The study nurses will provide the same asthma discharge instructions (see attached instructions), except for those instructions specific to ICS use.

One week after study enrollment, the child's pharmacy will be contacted to determine any prescriptions for asthma medications that were filled. Delivery of a doser CT device, which is used to assess medication adherence, will occur approximately one week after study enrollment. Unlike in the ICS Prescription Arm, the doser CT device for children in the control arm will be used with their albuterol MDI. Although this data will not be used for analysis, it makes the control arm intervention similar to the intervention arm from the perspective of the study participants. Families will be called after two weeks to determine if there are any issues with device use. To ensure proper communication, a checking-in mailer will be sent out two weeks post-enrollment. This mailer will serve as a reminder to contact staff if participants encounter any issues with the doser CT device or if their contact information has changed. A home visit will be scheduled at one month to arrange for retrieval of the doser CT device. An "Unable to Contact Mailer" will be sent out to participants if staff are unable to contact them after several attempts.

### **Summary of Intervention and Control Protocol**

Timing after enrollment	Study Procedure	Purpose	Intervention Arm	Control Arm
--	------------------------	----------------	-----------------------------	------------------------

Just prior to ED discharge	Study nurse performs discharge instructions; ICS prescription arm provides preferred pharmacy info	To provide education to both arms (ICS specific for ICS Prescription Arm)	X	X
Within 24 hours	Study clinician (PI) calls preferred pharmacy	To arrange ICS prescription	X	
Within 7 days	Researcher contacts pharmacy	To determine which participants filled an ICS prescription	X	X
One week	Research coordinator or RA arranges for home visit to deliver doser CT device*	To monitor medication adherence	X	X**
Two weeks	RA calls families who received Doser CT devices. A two week checking-in mailer is sent out.	To discuss any problems with the Doser CT device and changes in contact information.	X	X
One month	RA arranges home visit to retrieve Doser CT devices*	Retrieve CT Doser device	X	X
One, Two and four months	RA calls family	To reduce attrition and keep family excited about study	X	X
Six months***	Blinded researcher follow-up phone call	Outcome data collection	X	X

\* Participants will be mailed \$20 compensation for their effort upon completing the 6 month follow-up.

\*\* In Control Arm, Doser CT device will be used with albuterol MDI as sham intervention.

\*\*\* If follow-up phone call is unsuccessful, researcher will attempt home visits to collect outcome data.

**6 Month Follow-up Phone Call and Outcome Variables:** Six months after study enrollment, all participants will be contacted by telephone to collect outcome data. The researcher making the follow up phone calls will be blinded to the study arm of the participants. Telephone calls to participants will continue until follow up is complete, or further participation is refused. Informed consent at the time of enrollment will include permission to perform home-visits if telephone contact is unsuccessful. Participants will be mailed \$20 compensation for their effort upon completing the 6 month follow-up.

Outcome data collected will include unscheduled doctor's office visits, ED visits, hospitalizations, or oral steroid courses for asthma in the 6 months following enrollment. Unscheduled doctor's visits will be corroborated by contacting the child's primary doctor and obtaining a visit history (using the Release of Information form signed during consent). Visits in the week following enrollment will not be included as they will be considered part of the initial exacerbation. To corroborate oral steroid courses, we will contact the participant's pharmacy, using the Release of Information signed during consent.

Another outcome variable collected using a script during the telephone call will be the quality of life, using the ITG-CASF. The ITG-CASF has been validated in the ED setting for children 2 to 17 years old (34), is reliable (Cronbach's  $\alpha = 0.70$ ), can be administered by telephone (34), requires only 10 questions, and has been used in studies with similar follow up timeframes.(10) Each item is rated on a 5-point scale. Each response is scaled as a percentage of the maximum response, and the total score is the maximum percentage based on the number of questions answered. The scores range from 0 – 100, with higher scores reflecting better quality of life. The change in ITG-CASF scores for children with improved overall clinical status are 10 points higher than when children have not improved.(34)

**Data Analysis Plan:** Participants will be analyzed in the group to which they were randomized using an intention-to-treat approach. We hypothesize that children in the intervention arm will have less unscheduled health care use at 6 month follow up, and increased quality of life compared to children receiving routine asthma care. We will use chi-square testing for the health care use variable, and Student's t-test for the continuous quality of life variable.

**Power Analysis:** Sample size was calculated to power hypothesis testing for dichotomous health care use outcomes as they require the largest sample size. Using preliminary data to estimate baseline health care use in our study population,(35) we calculated the sample size needed to detect a difference in the proportion of children with unscheduled health care use in the intervention arm

( $p_1=0.35$ ) compared to the routine asthma care arm ( $p_0=0.6$ ), with 80% power to detect a statistically significant difference at an alpha of 0.05. Assuming 20% of participants will not be reached for follow up, and who will not have outcome data available when electronic medical records are audited, we will recruit 143 participants to achieve our sample size of 114.

**Data Safety and Monitoring Plan (DSMP):** The goals of the DSMP are three-fold. First, it is to ensure that there is no statistical difference in adverse events between the two study arms. Second, all serious adverse events will be reviewed by the members to provide direction on study continuation. Serious adverse events are considered very unlikely with this study protocol, since the two treatment conditions are both commonly utilized treatments in clinical practice. The third goal is to ensure that the intervention arm is not performing significantly better than the routine asthma care arm, as if this was identified early in the study, it would be unethical to withhold the intervention from the control arm.

Prior to beginning enrollment, we will have a conference call at which time the DSMP will be reviewed by the study PI and 2 Emergency Medicine attendings not affiliated with the study. The first DSMP data review will occur 6 months after the first participant has their 6 month data collection. Therefore this meeting will likely occur 12 months after study enrollment begins. Reviews will occur every 6 months thereafter.

The following outcome data will be provided to the DSMB along with the randomization assignments:

- Unscheduled medical visits to primary doctor's office for asthma
- ED visits for asthma
- Hospitalization for asthma
- Oral steroid courses for asthma
- Quality-of-life scores from the ITG-CASF
- Adverse events reported by parents at 6 month follow-up phone call
- Adverse events reported by study personnel
- Serious adverse events reported by study personnel\*

\* Any serious adverse events will be reported within 24 hours of occurrence to the IRB and DSMB. Study enrollment will be suspended until the DSMB and IRB have reviewed the event and made recommendations to the study PI.

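### The health care use outcome is tested with an unadjusted chi-square although age and graded baseline PACCI responses are in hand; adjusting for them would cost almost nothing, but the gain depends on a prognostic strength the documents do not give.

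*Combined protocol and SAP*

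**What the plan says.** The Data Analysis Plan sets out an intention-to-treat comparison and gives one test for this outcome: "We will use chi-square testing for the health care use variable". It names no covariate and no adjusted analysis.

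The Randomization section says "We will use block randomization to balance the number of participants in each arm", with block sizes of 4 to 8, and "The allocation ratio between intervention and control arms will be 1:1". It names no stratification factor, so the blocks balance numbers and leave prognosis to chance.

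The Participants section says "After consent, the participant and their family will complete the PACCI". Children whose responses show controlled asthma go no further; the others are randomized. Date of birth is recorded for each participant. The Project Background describes the PACCI as covering "questions about asthma over sub-acute (1-2 weeks) and longer (12 month) time periods".

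The Power Analysis takes proportions with unscheduled use of 0.35 (intervention) and 0.60 (routine care), "with 80% power to detect a statistically significant difference at an alpha of 0.05". It arrives at 114 children with outcome data, from 143 recruited.

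**The concern.** In a trial of this size, baseline variables that predict the outcome can do two things that a 2x2 table cannot: take explained variation out of the error, and correct the estimate when the arms differ by chance on those variables. PACCI responses cover recent symptoms and the past year, so it is plausible that they carry information about unscheduled use in the next 6 months. Age may carry some too. Both are available at no cost to the families. Planned power is close to 80% at best, so any precision available from data already collected is worth having.

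Timing matters as well. Under the Data Safety and Monitoring Plan, outcome data go to the board together with the treatment assignments, first at about 12 months after enrollment begins and every 6 months after that. An adjusted analysis that is not fixed in advance would look post hoc, however sound it was.

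**Working it through.** **Inputs.** p1 = 0.35, p0 = 0.60, 80% power, alpha 0.05, 114 evaluable (57 per arm), 20% loss (Power Analysis); 1:1 allocation (Randomization); uncorrected chi-square (Data Analysis Plan). Sidedness and continuity correction are not stated. I assume a two-sided, uncorrected test. The proportion of outcome variance explained by PACCI responses and age (R²) is not in the documents, so it is an assumption shown over a range.

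**Step 1: the plan's own figure.** With p̄ = 0.475, the pooled two-proportion power is

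Φ{[0.25·√n − 1.960·√(2·0.475·0.525)] / √(0.35·0.65 + 0.60·0.40)} = Φ{[0.25·√n − 1.384] / 0.684}.

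At n = 57: (1.887 − 1.384)/0.684 = 0.736, so power is 76.9%. Exact enumeration of the Pearson test gives 76.8%. Solving for 80%: n = (1.384 + 0.842·0.684)²/0.0625 = 61.4, that is 62 per arm or 124 in all. So 114 is not reproduced under this reading. The dropout step is correct: 114/0.8 = 142.5, rounded up to 143.

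**Step 2: effect of adjustment, by approximation.** Effective n per arm = 57/(1 − R²), put into the formula above.

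| Assumed R² | Effective n per arm | Approximate power |
|---|---|---|
| 0 | 57.0 | 76.9% |
| 0.02 | 58.2 | 77.8% |
| 0.05 | 60.0 | 79.0% |
| 0.10 | 63.3 | 81.2% |
| 0.15 | 67.1 | 83.4% |

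**Step 3: check by simulation.** The approximation comes from linear models, so it was checked with a logistic model containing arm and one normally distributed covariate: 57 per arm, marginal rates held at 0.60 and 0.35, 6,000 runs per setting. The test was of the arm coefficient.

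| R² | Approximation | Simulated chi-square | Simulated adjusted logistic |
|---|---|---|---|
| 0 | 76.9% | 77.4% | 77.3% |
| 0.020 | 77.8% | 77.2% | 77.9% |
| 0.053 | 79.2% | 76.5% | 78.7% |
| 0.119 | 82.0% | 76.2% | 80.7% |
| 0.192 | 85.2% | 77.2% | 85.3% |

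The Monte Carlo standard error is √(0.8·0.2/6000), about 0.5 point. The direction agrees throughout, and a useless covariate cost no detectable power.

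**Step 4: R² needed for 80%.** From Step 1, 1 − 57/61.4 = 0.07. Interpolating the simulated values between R² 0.053 (78.65%) and 0.119 (80.67%) gives 0.053 + 0.066·(1.35/2.02) = 0.097. Half a point of simulation error moves this by about 0.016, to 0.11. A fair range is 0.07 to 0.11.

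**Step 5: chance imbalance.** The standard error of a standardized covariate difference is √(2/57) = 0.187. A difference of at least 0.2 SD in a given covariate therefore has probability 2·[1 − Φ(0.2/0.187)], about 29%. The within-arm outcome SD is √(0.4675/2) = 0.483. With R² of 0.05 or 0.10, that imbalance shifts the estimated risk difference by 0.2·√R²·0.483 = 0.022 or 0.031, against a planned difference of 0.25.

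**Step 6: which PACCI variable can be used.** The only PACCI split the documents apply is controlled versus not controlled, and the controlled children are removed before randomization. That variable is constant among those analyzed. Only grading of the responses within the not-controlled group can explain variance, and over a restricted range.

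**Step 7: model size.** Expected events are 57·0.35 + 57·0.60 = 54 among 114. With arm and two covariates, that is 18 events per coefficient.

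**The case against.** The strongest reply is that nothing here is an error. An unadjusted intention-to-treat chi-square in a 1:1 randomized trial controls type I error and matches the calculation that set the sample size. Chance imbalance is already allowed for in that error rate, and with no stratification factor the design does not oblige anyone to adjust. All of this stands. A reader might infer that the chi-square is invalid or that the result will be biased; the documents do not support that.

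Second, the loss of precision is not demonstrated. No section links PACCI responses or age to later health care use; the validation reported in the Project Background concerns how accurately clinicians identify poor control, not prognosis. Low values of R² are plausible, because every randomized child is 3 to 12 years old, in the ED with an exacerbation, not controlled and not using an ICS. At R² = 0.02 the gain is under one point. This also stands, and it is why the gain is stated only as conditional.

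Third, the power shortfall belongs to the Power Analysis, not to the choice of test. It is small and depends on assumptions: 78.8% with an unpooled variance, 85.6% if the test were one-sided, and 85.7% if all 143 children (71.5 per arm) were followed rather than allowing for the loss in "Assuming 20% of participants will not be reached for follow up". This stands too. It does not remove the point, because a valid test can still be improved at almost no cost.

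**Conclusion.** The plan omits an inexpensive improvement; it does not contain an invalid analysis. The supported conclusion is that the chi-square forgoes precision to whatever extent age and graded PACCI responses predict 6-month unscheduled use. Under assumed R² of 2% to 15%, approximate two-sided power at 57 per arm rises from 77% to between 78% and 83%, and the simulations suggest the approximation is somewhat generous in the middle of that range.

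Two stronger readings are tempting. One is that adjustment would restore the stated 80%. That needs R² of about 0.07 to 0.11, and the documents offer no figure from which to judge whether it is reached. The other is that adjusting for PACCI control status would help. It cannot, because that status is the entry criterion.

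The figures rest on a two-sided uncorrected test, 57 evaluable children per arm, the planned rates of 0.60 and 0.35, and the assumed R². The simulations used a single covariate and tested the log odds ratio rather than the standardized risk difference, so they indicate size and are not an exact power for the analysis proposed below.

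**What to change.** Amend the Data Analysis Plan before any outcome data are seen by arm:

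- Make the primary analysis of this outcome a logistic regression of any unscheduled use on arm, age (continuous) and a graded score from the baseline PACCI responses. Write down how the score is formed, since the documents do not give the PACCI scoring. Do not use the controlled/uncontrolled category.
- Report a standardized risk difference with a 95% confidence interval from a robust or bootstrap variance. This keeps the target as the 0.60 versus 0.35 contrast rather than a conditional odds ratio.
- Keep the unadjusted chi-square as a supportive analysis, and state its sidedness.
- Date the amendment relative to the data reviews. If outcomes have already been reviewed by arm, the covariates should be fixed by someone who has not seen those data.

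The cost is a few sentences of plan and slightly more programming, with no new data and no extra children. The downside is that the gain may be only about one point if the covariates are weakly prognostic. This change does not replace correcting the stated power or sample size in the Power Analysis, which should be done separately.

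### The quality-of-life t-test has no stated use for the baseline ITG-CASF; ANCOVA on the 6-month score would be a free, modest gain if baseline precedes assignment

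*Combined protocol and SAP*

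**What the plan says.** Better quality of life in the intervention arm is one of the two hypotheses in the Data Analysis Plan. The only analysis named for it is Student's "t-test for the continuous quality of life variable". No covariate is mentioned.

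The section on the 6-month call introduces the measure thus: "Another outcome variable collected using a script during the telephone call will be the quality of life, using the ITG-CASF". The natural reading is that the 6-month scores are compared. The text does not rule out change scores, and the one benchmark it cites concerns change: "The change in ITG-CASF scores for children with improved overall clinical status are 10 points higher than when children have not improved".

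A baseline exists. The Participants section says: "A baseline quality of life score will also be obtained using the Integrated Therapeutics Group Child Asthma Short Form (ITG-CASF"). That section mentions randomization before it lists the baseline data. The Randomization section has the research assistant take the next envelope at enrollment and "open the envelope to determine the assignment". Neither section says whether the baseline score is complete by then.

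One part of the document, between the background and the Protocol section, was not available for review.

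**The concern.** A baseline measurement of the outcome is often the most useful covariate in a trial of this size, and here it is already being collected. Leaving it out of the model gives a wider confidence interval than the data need, on a hypothesis for which the plan states no power: the sample size was set on the dichotomous health care use outcome.

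Two gaps in the text add to this. The plan does not say which score the t-test is applied to, and a change score could be much less precise than the 6-month score. The order of baseline and assignment is also open. A parent-reported score taken after the family knows the arm could be influenced by it, and adjusting for such a score could bias the comparison. The unadjusted test of 6-month scores does not depend on that order.

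**Working it through.** **Inputs from the documents.** Allocation is 1:1 (Randomization). Alpha is 0.05 (Power Analysis), taken here as two-sided. On numbers, the plan says: "we will recruit 143 participants to achieve our sample size of 114". The inflation reproduces: 114/(1 − 0.20) = 142.5, rounded up to 143. Half of 114 is 57 per arm. There is no stated quality-of-life power to reproduce.

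**Assumed inputs.** SD 20 (range 15 to 30), r from 0 to 0.5, and a difference of 10 points (also 5 and 7.5). The 10 points is borrowed from the benchmark for improved versus unimproved children. It is illustrative and is not a target of the trial.

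**Formulas** (n per arm)
- t-test on 6-month scores: SE = SD × √(2/n), df = 2n − 2 = 112.
- ANCOVA: the variance is multiplied by (1 − r²) × (1 + 1/(2n − 4)), df = 111. The second term, 1 + 1/110, is the cost of estimating the slope and is included in every ANCOVA figure below.
- Change score: the variance is multiplied by 1 + k² − 2rk, where k is baseline SD divided by 6-month SD.
- Power is from the noncentral t distribution. Equivalent N is 114 divided by the variance factor.

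**Worked case.** For the t-test, SE = 20 × √(2/57) = 3.746, the 95% CI half-width is 7.42 and power is 75.4%. For ANCOVA at r = 0.35, the factor is 0.8775 × 1.0091 = 0.8855, so SE = 3.746 × √0.8855 = 3.525, the half-width is 6.99 and power is 80.3%. Equivalent N is 114/0.8855 = 128.7.

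| Analysis | Power, 10 points, SD 20 | CI half-width | Equivalent unadjusted N |
|---|---|---|---|
| t-test, 6-month score | 75.4% | 7.42 | 114 |
| ANCOVA, r = 0 | 75.0% | 7.46 | 113 |
| ANCOVA, r = 0.2 | 76.7% | 7.31 | 118 |
| ANCOVA, r = 0.3 | 78.9% | 7.11 | 124 |
| ANCOVA, r = 0.35 | 80.3% | 6.99 | 129 |
| ANCOVA, r = 0.5 | 86.0% | 6.46 | 151 |

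The two analyses break even at r = √(1/111) = 0.095.

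**Sensitivity to SD** (10 points; SD 15, 20, 25, 30). The t-test has 94%, 75%, 56% and 42% power; ANCOVA at r = 0.35 has 96%, 80%, 61% and 47%.

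**Sensitivity to the difference** (SD 20; r from 0.2 to 0.5). For 5 points, power is 26% against 27% to 33%. For 7.5 points, it is 51% against 52% to 63%.

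**If change scores were meant.** At r = 0.2, power for 10 points is 55% with equal SDs (k = 1) and 65% with k = 0.75. Change scores are less precise than 6-month scores whenever r < k/2.

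**Missing baselines.** In a simulation with 10% of baselines missing at random and replaced by the pooled mean (20,000 runs per case, normal scores), type I error was 0.048, 0.049 and 0.047, and power 76.3%, 79.8% and 84.6%, at r = 0.2, 0.35 and 0.5.

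**The case against.** The strongest reply is that nothing is broken. An unadjusted t-test in a 1:1 randomized trial is an accepted analysis, quality of life does not set the sample size, and every quantity that sets the gain is assumed. The documents also hint that r is low. Baseline is taken during an acute episode. Children whose asthma the PACCI rates as controlled are not randomized, which may narrow the baseline range. The instrument's Cronbach's alpha is 0.70; if that approximates its reliability at both times, an observed r of 0.5 needs a true correlation of about 0.5/0.70 = 0.71. At r = 0.2 the gain is 1.3 power points. This stands as a limit on size: the upper end of the range should not be relied on. It is not a reason against the change, because the loss at r = 0 is only about 0.4 points.

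The number analyzed may also fall short of 57 per arm. The 20% loss allows for outcomes recovered from record audit, which cannot supply an ITG-CASF score. At an assumed 50 per arm, power is 70% for the t-test and 75% for ANCOVA at r = 0.35. The absolute powers drop, but the proportional gain hardly moves.

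That the baseline goes unused is inferred from silence. If the t-test was meant for change scores, the baseline is used. ANCOVA would then still be at least as precise, apart from one degree of freedom, and the plan would still need to say which score is tested.

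Finally, if enrollment is under way, the order of baseline and assignment may not be recoverable. That is a fair limit, and the fallback in the fix covers it.

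**Conclusion.** The point holds as an improvement that should be made, not as the correction of an invalid test. The omission is clear in the text available for review. With 57 per arm, SD 20 and a 10-point difference, ANCOVA adds about 1 to 11 power points over r = 0.2 to 0.5 and narrows the CI half-width from 7.42 to between 7.31 and 6.46. The lower part of that range is the more plausible. The proportional gain depends on r and hardly on SD or sample size; the absolute powers depend on all the assumed values. The benefit is conditional on baseline being recorded before assignment is known.

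**What to change.** Replace the quality-of-life sentence in the Data Analysis Plan with: *6-month ITG-CASF will be compared between arms by linear regression (ANCOVA) adjusting for baseline ITG-CASF, reporting the adjusted mean difference and 95% CI; a missing baseline will be replaced by the mean baseline of both arms combined. The unadjusted difference in 6-month scores will be reported as a sensitivity analysis.*

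In the Participants and Randomization sections, state that the baseline ITG-CASF is obtained before the assignment envelope is opened. If that order cannot be confirmed for children already enrolled, if any, keep the unadjusted comparison of 6-month scores as the main quality-of-life analysis.

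Date the change, including the choice between ANCOVA and the fallback, before those deciding on it see scores by arm. The monitoring plan supplies ITG-CASF scores with assignments at its periodic reviews, so this needs attention. The chi-square analysis of health care use stays as it is.

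The cost is two sentences in the analysis plan, one in the enrollment procedure (which can bind only children not yet enrolled), one degree of freedom, and no new data or recruitment.
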